**The Effect of Synbiotic Tablet Usage on the Clinical and Biochemical
Parameters in Smokers and Nonsmokers with Gingivitis: A Randomized
Placebo-Controlled Clinical Trial**

Document Date: February 27, 2018

Study Design

This study designed as a double-blind randomized placebo-controlled clinical trial.

Participants were primarily divided into two groups according to their smoking and non-smoking status. Then both groups in itself were randomly assigned again into two groups as test and control groups. Randomization was performed by one researcher that had never any role in participant's treatment and clinical measurement processes ([name]). Random selection was made in first person's participation by coin toss and then next participant was included into the other group according to previous participant's group. Four groups in this study are shown below:

- Smoker(+), test group(T) given synbiotic tablets; (T(+))
- Smoker(+), control group(C) given placebo tablets; (C(+))
- Non-smoker(-), test group(T) given synbiotic tablets; (T(-))
- Non-smoker(-), control group(C) given placebo tablets; (C(-))

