In the screening phase, clinical measurements were carried out as an initial evaluation and in the next visit biochemical and microbiological samples were collected for baseline examination and all participants were received mechanical debridement procedure including tooth-polishing (rubber-cup and abrasive paste) and scaling by the help of ultrasonic devices §§ and periodontal hand pieces ¶¶ before the experimental period. On the day of periodontal treatment each subject was instructed to chew one test or placebo tablet that was given according to their groups, per day, during 30 days. Test and placebo tablets were prepared to have the same characteristics in terms of shape, color, taste and size. Commercially available Probiotic Chewable Tablets ¶¶ (Table 1) were used in the test group and a placebo tablet had been prepared to same company with similar content with the test tablets but does not contain microorganisms. Oral hygiene training with tooth brush and floss was given to all participants. They were also instructed not to take other probiotic products throughout the test period. Clinical parameters including PI (28) and GI (29) and GCF samples had been obtained from all subjects on days 0 (baseline), 30 (1st month), and 60 (2nd month). Patients' professional supragingival plaque control was made in the control session of 1st and 2nd month. Side effects were recorded by patients'

verbal statement. Patients' all measurements and treatments were made by a single researcher who doesn't know in which group participants were included ([name]).

Biochemical Analysis

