**Document Date: February 27, 2018**

## Statistical Analysis

The suitability of the normal distribution of the variables in our study was evaluated with graphical and Shapiro-Wilks test. The median (minimum, maximum) was used to display the descriptive statistics of variables identified as an abnormal distribution. Number (n) and percentage values were given to show the distribution of categorical variables like gender.

Kruskal-Wallis non-parametric analysis of variance was used to examine if there has been any discrepancy in the values of the clinical and biochemical measurements at baseline, 1st month and 2nd month. Bonferroni correction with the dual comparisons were made to determine the group causing variations in the variables found significant differences as result of Kruskal-Wallis test.

For comparing the clinical, biochemical and microbiological measurements at baseline, 1 month and 2 months in each group (T(+) T(-), C(+), C(-)) Friedman non-parametric repeated measures analysis of variance was used. Bonferroni correction double comparisons were made in variables determined statistically significant differences from the result of the Friedman test.

G\*Power pack program\*\*\* was used in order to determine the number of samples used in the study. For the width effect f: 0.25, type-I error probability  $\alpha$ :0.05, type-II error probability  $\beta$ : 0.05 and power: 0.95, at least 15 sampling units have been calculated to include in the study for each group. At least 5 subjects were added for each group considering the missing data that was deemed to occur during the course of follow-up. Sample size calculation was attempted based on the primary outcome measure.

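### The supplied text names no primary outcome, visit or contrast and no error control across 10–12 outcome-visit results, and the stated 95% power matches a test that the plan does not contain

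*SAP*

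**What the plan says.** All of the statistical text is in the SAP under Statistical Analysis.

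- **Primary outcome.** The sample size paragraph ends: "Sample size calculation was attempted based on the primary outcome measure". No supplied section of either document says which measure this is, at which visit, or for which comparison.
- **Sample size.** The inputs begin "For the width effect f: 0.25, type-I error probability" and continue with 0.05 for type I error and 0.95 for power. The result is that "at least 15 sampling units have been calculated to include in the study for each group", with at least 5 more per group for missing data.
- **Between groups.** Clinical and biochemical values at baseline, month 1 and month 2 go through Kruskal-Wallis tests. After a significant one, "Bonferroni correction with the dual comparisons were made to determine the group causing variations in the variables". The number of pairs is not given.
- **Within groups.** Each of the four groups is followed over the three visits by Friedman tests, and then "Bonferroni correction double comparisons were made in variables determined statistically significant differences from the result of the Friedman test". This list also includes microbiological measurements.
- **Outcomes and groups.** The Protocol (Study Design) says "Clinical parameters including PI (28) and GI (29) and GCF samples had been obtained from all subjects" at the three visits. Biochemical Analysis adds IL-6, IL-8 and IL-10, and says that GCF volume was recorded. Participants were split by smoking status, and then "both groups in itself were randomly assigned again into two groups as test and control groups".

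**The concern.** A primary outcome limits false positives only if the reader can tell which result it is. Here a synbiotic effect could be reported from any of five or six measures, at either of two post-baseline visits, in smokers or in non-smokers. The two Bonferroni steps each work inside a single omnibus test. Neither reaches across outcomes, and the between-group step does not reach across visits.

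The sample size does not settle the matter. It gives an effect size f with no outcome, difference or SD, and the analysis that best matches the stated 15 per group is not one the plan performs. At stake are the error rate behind any claim that the tablet works, and whether 95% power describes any comparison in the plan.

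**Working it through.** **1. The plan's own figure.** Inputs from the SAP: f = 0.25, alpha 0.05, power 0.95. From the Protocol: 4 groups, 3 visits. Assumed: correlation 0.5 between visits, and sphericity. For a group-by-visit interaction in repeated-measures ANOVA with N = 4n and m = 3, the noncentrality is λ = f²·N·m/(1 − ρ), with df 6 and 2(N − 4).

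- n = 15: λ = 0.0625 × 60 × 3 / 0.5 = 22.5, df 6 and 112, power 0.954.
- n = 14: λ = 21.0, df 6 and 104, power 0.937.

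So 15 is reproduced. At correlation 0.3 the same formula gives 21 per group, and at 0.7 it gives 10. The other variants at f = 0.25 do not give 15: one-way ANOVA needs 70 per group, repeated-measures between-group 47, and within-group 11 (the last two at correlation 0.5). For the one-way four-group comparison at n = 15, λ = 0.0625 × 60 = 3.75 with df 3 and 56, and power is about 0.32. Kruskal-Wallis at each visit is the rank counterpart of this one-way test. Neither it nor Friedman within each group tests the interaction.

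**2. Number of results.** PI, GI, IL-6, IL-8 and IL-10 at two post-baseline visits give 5 × 2 = 10; with GCF volume, 6 × 2 = 12. Four groups form six pairs, of which two compare synbiotic with placebo within a smoking stratum: T(+) with C(+) and T(−) with C(−).

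**3. Simple bounds.** Ignore the Kruskal-Wallis step and treat the results as independent.

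- Six pairs corrected: 1 − (1 − 0.05/6)^20 = 15.4% for 10 results, and 1 − (1 − 0.05/6)^24 = 18.2% for 12.
- Only the two tablet pairs corrected: 1 − 0.975^20 = 39.7% and 1 − 0.975^24 = 45.5%.

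Requiring a significant Kruskal-Wallis test first, or correlation among results, lowers these figures.

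**4. Simulation of the described procedure.** Normal data, no tablet effect, Kruskal-Wallis at 0.05, then pairs at 0.05/6. A claim is either tablet pair significant in either direction. There were 4,000 runs per setting. The documents give no correlations, smoking effect or pair test, so these were varied. The SAP gives 0.05 only in the sample size sentence. The table shows the chance of at least one false claim at 15 per group, as Dunn pairs / Mann-Whitney pairs.

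| Outcome/visit correlation | 12 results, no smoking effect | 10 results, no smoking effect | 12 results, smoking 1 SD | 10 results, smoking 1 SD |
|---|---|---|---|---|
| 0 / 0 | 15.2% / 13.4% | 13.4% / 12.3% | 6.1% / 14.8% | 5.6% / 13.2% |
| 0.3 / 0.5 | 14.1% / 12.1% | 12.0% / 10.4% | 6.4% / 15.2% | 5.3% / 11.7% |
| 0.5 / 0.5 | 12.1% / 11.0% | 10.4% / 9.0% | 5.3% / 11.7% | 4.6% / 10.1% |
| 0.7 / 0.7 | 10.3% / 9.3% | 9.5% / 8.0% | 4.6% / 10.0% | 3.7% / 9.2% |

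Over 15 and 20 per group the ranges are 8.0–15.6% with no smoking effect and, with a smoking effect of 0.8–1 SD, 3.7–9.4% (Dunn) or 8.4–15.2% (Mann-Whitney). One outcome at one visit carries only 0.5–1.5%. An independent simulation over similar settings gave 6–16% in either direction and 3–8% when only results favouring the tablet count; with Dunn pairs and a 1 SD smoking effect included, the favourable-only figure falls to about 1.7%.

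**5. Two ways to test the primary at an overall 0.05, n = 15 per group.** f = 0.25 can mean different shifts. As a two-arm effect, d = 2 × 0.25 = 0.5. As an interaction effect appearing after baseline in one stratum only, the shift is 0.25/(0.4330 × 0.4714) = 1.22 SD, where 0.4330 = √(1/4 × 3/4) for one group of four and 0.4714 = √(1/3 × 2/3) for the visits.

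| True effect | One stratified Wilcoxon test at 0.05 | Two stratum-specific Mann-Whitney tests at 0.025 |
|---|---|---|
| 0.5 SD in both strata | 45% | 29% |
| 1.22 SD in one stratum only | 53% | about 80% |

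**The case against.** The SAP refers to a primary outcome as though one existed, and part of the SAP was not in the supplied text. A reader might infer that none was chosen, or that it was chosen after the data were seen. The documents support neither inference. What stands is that the supplied text does not identify it.

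A reader might also infer that the plan always exceeds 5% error. It does not: with Dunn pairs, a large smoking effect and high correlations the figure falls below 5% even counting both directions, and counting only results favouring the tablet roughly halves the range. Nor is 0.05/6 the plan's rule, since no number of pairs is stated. That uncertainty cuts both ways, because correcting only the two tablet pairs would raise the error well above the range given.

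The match to an interaction test rests on an assumed correlation. Another correlation could make another model give 15, so this does not show that the sample size was miscalculated. It shows that the stated power cannot be tied to a test in the plan.

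It is tempting to argue that a pooled, stratified test must replace the plan's pairs because it has far more power. That comparison is unfair: the plan's pair rule runs at about 1% error for one result, and a stratified test at 0.05 runs at about 5%. Stratum-specific contrasts also fit a trial titled "Parameters in Smokers and Nonsmokers with Gingivitis" that allocates tablets within each smoking group. Which test is stronger depends on whether one or both strata respond.

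**Conclusion.** The concern holds in this form: the supplied text identifies no primary outcome, visit or contrast, and describes nothing that controls error across 10–12 outcome-visit results. This is more than a missing detail, because following the text as written leaves any of those results open to being reported as a tablet effect.

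The size is conditional. With six pairs assumed and both directions counted, at least one false synbiotic-versus-placebo result arises in about 8–16% of trials without a smoking effect and about 4–15% with a smoking effect of 0.8–1 SD. Within-group Friedman findings and microbiological outcomes are not in this count.

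The omission is certain for the supplied text; its numerical consequence is known only as a range. The stated 95% power should not be read as the power of any synbiotic-versus-placebo comparison in the plan.

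**What to change.** 1. State the one outcome, visit and synbiotic-versus-placebo contrast to which the sample size refers, using only a primary documented before unblinding.
2. Test it at an overall two-sided 0.05, either as one smoking-stratified test or as two stratum-specific tests at 0.025 each. Choose beforehand, and say whether the visit value or the change from baseline is analysed.
3. Control the remaining tablet comparisons, for example by Holm after a significant primary, or label them exploratory. With two primary tests at 0.025, only the alpha of those that succeed passes on.
4. If no primary was documented beforehand, apply Holm across all tablet comparisons or label all results exploratory.
5. State how many pairs the existing Bonferroni steps cover.
6. Restate power for the chosen test, with the assumed difference in SD units, and do not carry over the 95%.

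**Cost.** No new data. Secondary claims face stricter thresholds. With pooled and both stratum-specific tests at 12 outcome-visits there are 12 × 3 = 36 tests, or 35 after a stratified primary, and the first Holm step is 0.05/35 = 0.0014, against 0.05/6 = 0.0083 if six pairs are assumed. The restated power will probably be less favourable. Choosing the stratified test gives up power if one stratum alone responds; choosing two stratum-specific tests gives up power if both do.
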